1.1 Study Schematic

Abbreviations: bpm = beats per minute; CRC = Cohort Review Committee; COVID-19 = coronavirus disease 2019 (severe acute respiratory syndrome coronavirus 2 [SARS-CoV-2]); IV = intravenous; R = randomization; RP2D = recommended Phase 2 dose; SOC = standard of care

- a. Patients will be evaluated for enrollment during the up to 7-day screening period. The complete list of entry criteria is provided in Section 4.0.
- b. A CRC will review blinded safety, tolerability, pharmacokinetic, pharmacodynamic, and disease measurement data, make decisions about escalating or de-escalating the bempegaldesleukin dose, and identify the RP2D (see Section 7.16).
- c. If the CRC determines additional patients may be randomized, 2 patients will be randomized (1 with bempegaldesleukin/SOC and 1 with placebo/SOC), treated with study drug, and observed for 72 hours. For every 2 patients, the Medical Monitor will review the blinded safety and tolerability data for the first 72 hours after study drug administration to determine if the next 2 patients may be randomized (Section 5.3).
- d. The Safety Follow-Up should occur 30 days (\pm 7 days) after discharge from the hospital or in-patient facility. See Section 5.7 for additional details.

Protocol No. 20-214-34

Note. The Safety Follow-Up should occur 30 days (\pm 7 days) after discharge from the hospital or in-patient facility. See Section 5.7 for additional details.

a. Earliest possible randomization day for the next eligible patients if approved by CRC (see Section 5.3).

b. Earliest possible randomization day for the next eligible patients if approved by Medical Monitor (see Section 5.3).

1.2 Schedule of Events

Procedure / Period:	Screening	Т	reatment	Post-Treatment
Study Days ^a :	Days –7 to –1	Day 1	Days 2+ until Discharged ^a	Safety Follow-Up 30 days after discharge (± 7 days)
Informed consent	Х			
Inclusion/ exclusion criteria, including documentation of positive SARS-CoV-2 infection	х			
Medical history	Х			
Randomization		Predose		
Physical examination ^b	Х	Predose	Every day	
Vital signs, including SpO2 ^c	Х	Predose	Every day	
ECG ^d	Х			
Clinical data collection ^e		Predose	Every day	Call to patient ^r
Laboratory Assessments ^f		•		
Hematology and chemistry ^g	X (local lab)	Predose ^h (central lab)	Days 2, 3, 4, 6, 8 (central lab) ^j	
Coagulation ^g	X (local lab)	Predose ^h (central lab)		
Additional laboratory assessments	X (IL-6: local or central lab; other assessments: local lab)	Predose ^h (central lab)		
Serology HIV/HBV/HCV	X (local lab)			
Pregnancy test ^k	X (local lab)		Day 8 (local lab) ^j	
Urinalysis (dipstick)		Predose ^h (local lab)		
PK assessments ¹		Predose ^h and EOI ⁱ	Days 2, 3, 4, 6, 8 ^j	
Immunogenicity assessments ¹		Predose ^h	Day 8 ^j	Collect sample ^s

Schedule of assessments continued on next page.

Procedure / Period:	Screening	Treatment		Post-Treatment
Study Days ^a :	Days –7 to –1	Days 2+ until Day 1 Discharged ^a		Safety Follow-Up 30 days after discharge (± 7 days)
Biomarkers (central laborator	y only)	,	,	
Respiratory specimens for detection of SARS-CoV-2 nucleic acid ^{m,n}		Predose ^h	Days 4 and 8 ^j	Collect sample ^s
SARS-CoV-2 serology ^m		Predose ^h	Days 4 and 8 ^j	Collect sample ^s
HLA Haplotyping ^m		Predose ^h		
DNA/RNA sequencing ^m		Predose ^h	Days 4 and 8 ^j	Collect sample ^s
Immune cell profiling ^m		Predose ^h	Day 8 ^j	Collect sample ^s
Cytokine assessments ^m		Predose ^h	Days 2, 3, 4, 6, 8 ^j	
Study Drug Administration				
Study drug administration °		Х		
Hydration		X ^p	Days 2-4 ^p	
Standard of care ^q		As clinically indicated		
AE assessment	Х	Х	X ^t	Call to patient ^r
Review of concomitant medications	Х	Х	\mathbf{X}^{t}	Call to patient ^r

Table 1:Schedule of Events (Contd)

Abbreviations: AE = adverse events; ECG = electrocardiogram; EOI = end of infusion; HBV = hepatitis B virus; HCV = hepatitis C virus; HIV = human immunodeficiency virus; HLA = human leukocyte antigen;

PK = pharmacokinetics; SARS-CoV-2 = severe acute respiratory syndrome coronavirus 2; SpO₂ = oxygen saturation

- a. Patients must remain in the hospital or be admitted to an in-patient facility for monitoring until at least Day 8. Study assessments may be delayed or moved ahead of the window to accommodate unforeseen delays after permission from the Medical Monitor. All procedures and examinations should be performed before the administration of study drug, except as indicated.
- b. Physical examination will include a full physical examination at Screening and on Day 1 (prior to dosing) and targeted physical exams on other days; see Section 7.13.
- c. Vital sign assessments for Day 1 must occur prior to administering study drug. See Sections 5.5.4.1 and 7.14.
- d. ECG must be done within 7 days prior to Day 1. See Section 7.15.
- e. Clinical data to be collected include:
 - Clinical support measures (eg, oxygen requirement) and physical activity limitations, see Section 8.1.1.
 - WHO Clinical Progression Scale, see Section 8.1.2.

Laboratory Assessments and Biomarkers:

- f. Safety laboratory assessments are categorized in two groups depending on the purpose:
 - For local laboratory assessments collected in this study, see Appendix 1A.
 - For central laboratory assessments collected throughout the study, see Appendix 1B.
- g. Hematology, serum chemistry, and coagulation assessments should be drawn in the morning.
- h. Predose samples should be collected up to 3 hours before study drug administration.
- i. End of infusion samples should be collected within 30 minutes of the end of study drug infusion.
- j. If the patient is discharged from the in-patient facility prior to Day 6, a sample will be collected between Days 6 to 10, inclusive. If the patient is unable to return to the clinic, samples may be collected by research staff or designee at an alternate location.
- k. See Section 7.11.1.
- 1. See Section 5.10.
- m. All biomarker samples should be drawn in the morning. See Section 5.11 for additional details.
- n. Collect oropharyngeal and anterior nares or nasopharyngeal swabs according to the CDC guidelines (CDC 2020b).

Study Drug Administration:

- o. See Sections 5.5.1 and 5.5.2 for additional details.
- p. Patients should receive IV fluid as tolerated on the day of dosing (Day 1) and continue with oral hydration as tolerated for the subsequent 3 days. In the event patients cannot adhere to the oral hydration guidelines, IV hydration should be administered as clinically indicated. If the patient is prematurely discharged from the in-patient facility before Day 4, contact the patient (by telephone or clinic visit) once between Days 2 to 4, inclusive, to remind the patient of the oral hydration guidelines and to assess for any symptomatology and compliance with the hydration guidelines. Site personnel must document the hydration and the results of the discussion. Additionally, advise patients who are discharged from the in-patient facility before Day 8:
 - To restrain from activities that may contribute to dehydration (including, but not limited to, strenuous activity, long hot showers, and saunas) from Days 1 to 8.
 - If experiencing orthostatic symptoms, the patient should contact site personnel and consider increasing oral hydration.

See Section 5.5.4.2 for additional details.

- q. See Section 5.5.3 for additional details.
- r. The Safety Follow-Up call should occur 30 days (± 7 days) after discharge from the hospital or in-patient facility. If the patient remains at the in-patient facility after Day 8, the Safety Follow-Up call should occur no later than 38 days (± 7 days) after Day 1, the day of study drug administration. See Section 5.7 for additional details.
- Samples will be collected 30 days (± 7 days) after hospital or in-patient facility discharge for immunogenicity, DNA/RNA sequencing, SARS-CoV-2 serology, immune cell profiling, and detection of SARS-CoV-2 nucleic acid. Note:
 - If the patient is unable to return to the clinic, samples may be collected by research staff or designee at an alternate location.
 - If the patient remains at the in-patient facility after Day 8, samples should be collected no later than 38 days (± 7 days) after Day 1, the day of study drug administration.

See Section 5.7 for additional details.

t. If the patient is prematurely discharged from the in-patient facility, site personnel should contact the patient by telephone each day until Day 8 for collection of AEs and concomitant medications.

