2.1.3.1 Bempegaldesleukin Mechanism of Action, Pharmacokinetics and Pharmacodynamics

Bempegaldesleukin is an immunotherapeutic protein prodrug with unique properties specifically designed to activate the immune system by providing a controlled, sustained signal to the IL-2 receptor pathway.

Bempegaldesleukin contains aldesleukin conjugated to 3 to 8 polyethylene glycol (PEG) groups, with an average of 6 PEG groups per aldesleukin. In this fully pegylated prodrug form, bempegaldesleukin is inactive. After administration in vivo, PEG groups release to form various PEG-IL-2 species composed of releasable and stable PEG groups. Active cytokines are composed of releasable and stable 2-PEG-IL-2, releasable and stable 1-PEG-IL-2, and IL-2 (Figure 3) that have a peak plasma concentration 26 to 48 hours after infusion.

Figure 3:Release of PEG Groups from Bempegaldesleukin to Form Active
Cytokines

* Bempegaldesleukin drug product contains an average of six PEG molecules.

The slow generation of the 2-PEG-IL-2 and 1 PEG-IL-2 significantly mitigates the rapid-onset of systemic cytokine-related toxicities associated with high dose IL-2. In vitro hydrolysis studies demonstrate PEG release occurs sequentially, with a half-life of 20 hours for each step in the release, supporting the lack of a "burst" IL-2 release (Charych 2016). Therefore, slow release of

Nektar Therapeutics Confidential and Proprietary PEG relative to fast clearance of IL-2 results in predominant exposure to active pegylated IL-2 conjugates.

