2.1.4.2.3 Risk Period for Bempegaldesleukin Active Compounds

Bempegaldesleukin is a prodrug. The periods when AEs associated with bempegaldesleukin are most likely to appear are 1) during or shortly after completion of the IV infusion and 2) approximately 2-4 days following the infusion. Reactions during or after the infusion period typically manifest as transient flushing, chills, itching, rash, and flu-like symptoms. The principal period of risk is when the prodrug releases the active moieties. These active forms gradually increase after dosing and peak between 24 and 48 hours post-dose.

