2.1.4.2.5 Hypotension and Capillary Leak Syndrome

No patients in studies of bempegaldesleukin have experienced capillary leak syndrome.

Hypotension has been characterized as an identified risk of bempegaldesleukin. Instances of hypotension appear around 1-4 days following the infusion of bempegaldesleukin, coinciding with the peak plasma concentration of the active pegylated IL-2 conjugates formed after administration of bempegaldesleukin (NKTR-214-AC). Patients with bempegaldesleukin-induced hypotension are usually rapidly responsive to fluid administration.

Importantly, while AEs of hypotension occurred in 2 of the 4 patients who received monotherapy with 0.003 mg/kg bempegaldesleukin, the lowest dose administered to date, none were higher than Grade 2 severity. By comparison, the starting dose of bempegaldesleukin in the amended Study 20-214-34 is 0.00075 mg/kg, ie, one-fourth the dose at which Grade 1 or 2 hypotension was observed in 2 patients. Dose selection for this study is discussed further in Section 2.2.4.

A specific management guideline, including prophylactic fluid administration, was implemented in ongoing bempegaldesleukin studies, which has successfully mitigated the risk of hypotension (refer to Section 6.2 [Warnings and Precautions] of the bempegaldesleukin Investigator's Brochure).

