5.5.2 Study Drug Dosing

Each patient's dose of study drug will be determined by the patient's dose cohort and weight in kilograms, which will be determined on the day of study drug dosing.

Patients should receive study drug at the starting dose determined by the patient's dose cohort on Day 1. Study agent(s) should be administered in an area with access to resuscitation equipment.

Study drug will be administered IV over 15 (\pm 5) minutes. The duration of infusion of study drug may be increased if necessary (eg, patient history of infusion reaction) (see Pharmacy Manual for details). The study drug infusion must be promptly followed by a flush with diluent to clear the IV line to ensure the full dose is administered. The total volume of study drug infusion should include the flush of diluent.

Patients should be carefully monitored for infusion reactions during study drug administration. If an acute infusion reaction is noted, patients should be managed according to the guidelines in Section 5.6.2.

Please refer to the Pharmacy Manual/current Investigator's Brochure for details regarding study drug reconstitution, preparation, storage, and administration.

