5.5.4.1 Vital Signs

Refer to Section 7.14 for vital sign measurements, which are to be monitored according to the Schedule of Events (Section 1.2).

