5.12 Prior and Concomitant Medications

All medications (prescription and over the counter [OTC]), vitamin and mineral supplements, and/or herbs taken by the patient from Screening through the Safety Follow-Up call will be documented and recorded, including start and stop date, dose and route of administration, frequency, and indication. Medications taken for a procedure (eg, venipuncture) or prophylaxis of an infusion-related reaction should also be included.

Details regarding IV hydration will be recorded in the EDC.

5.12.1 Prophylaxis and Management of Symptoms Related to Immediate Infusion-Related Reactions (including Flu-Like Symptoms and Hypersensitivity Events)

Prophylactic treatment with a nonsteroidal anti-inflammatory, antipyretic, and antihistamine medications for flu-like symptoms and hypersensitivity events (eg, rash and/or pruritis), respectively, is recommended prior to bempegaldesleukin infusion at the discretion of the Investigator.

For post-infusion, flu-like symptoms and hypersensitivity events, treatment with nonsteroidal anti-inflammatory, antipyretic, and antihistamine medications may continue at the Investigator's discretion to manage the patient's symptoms. Additional treatment measures may be administered based on local treatment standards and guidelines, see Section 5.6.2.

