7.0 ASSESSMENT OF SAFETY

7.1 AE Definition and Assessment

An AE is defined as any untoward medical occurrence in a clinical investigation patient administered a pharmaceutical product, at any dose, not necessarily related to the treatment.

An AE can therefore be any unfavorable and unintended sign, symptom, or disease temporally associated with the use of a medicinal product, whether or not considered related to the medicinal product. An AE can also arise from any use of the drug and from any route of administration, formulation, dose, or overdose. This definition includes intercurrent illnesses or injuries, and exacerbation of preexisting conditions. Clinical laboratory, vital sign, or physical examination abnormalities will only be reported as AEs if they are deemed clinically significant by the Investigator (eg, associated with signs and symptoms, require treatment, or require follow-up).

An AE does not include:

- Pre-existing diseases or conditions present or detected before start of study drug(s) administration that do not worsen or increase in severity or frequency after the administration of study drug(s).
- Overdose of either study drug(s) or concomitant medication without any signs or symptoms.

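### No vital signs are scheduled on Day 1 after dosing, so the acute infusion window has no planned measurement; one timed set at the existing end-of-infusion PK draw would fill it

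*Protocol*

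**What the plan says.** In Table 1 (Protocol 1.2) the vital-signs row, which includes SpO2, reads predose for Day 1 and every day from Day 2 to discharge. Footnote c fixes the Day 1 timing: "Vital sign assessments for Day 1 must occur prior to administering study drug". Footnote a makes predose the default for all procedures unless something else is indicated, and nothing else is indicated for vital signs. Footnote c cites Sections 5.5.4.1 and 7.14, but neither adds a time point; both refer back to the Schedule.

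Section 2.1.4.2.3 gives the two periods when drug-related events are most likely: "1) during or shortly after completion of the IV infusion and 2) approximately 2-4 days following the infusion". It calls the second, when active moieties are released, the principal one. Section 5.6.2 says that infusion reactions have been reported and lists fever, hypotension, hypertension and bronchospasm among the possible signs.

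During dosing, Section 5.5.2 says: "Patients should be carefully monitored for infusion reactions during study drug administration". It names no measurement, time or recorded value. Section 7.1 limits what reaches the AE database: "Clinical laboratory, vital sign, or physical examination abnormalities will only be reported as AEs if they are deemed clinically significant by the Investigator".

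The PK row already has an end-of-infusion (EOI) sample on Day 1, due within 30 minutes of the end of infusion (footnote i). SAP 11.6 summarises vital signs at baseline and at each post-dose time point.

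**The concern.** Safety and tolerability of a single infusion against placebo is a primary objective. The protocol identifies an acute window of risk, and several of the signs it lists for infusion reactions (blood pressure, temperature, respiratory effects) are ones that the Section 7.14 vital-sign set would pick up. Yet the only Day 1 set comes before the drug, and the first post-dose set that SAP 11.6 can summarise is the Day 2 reading.

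Symptoms such as flushing, chills or rash do enter the TEAE tables by treatment, at any grade. A change in blood pressure, pulse or saturation that the Investigator does not judge clinically significant has no planned record in either arm. At stake is the completeness of the descriptive safety comparison in that window, not patient care and not a dosing decision.

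**Working it through.** The plan gives no figure for this point, so there is none to reproduce. The check is a count from the schedule, a timing calculation for the added set, a check of how SAP 5.1 would handle it, and its precision.

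**Scheduled sets in the acute window** (start of infusion to 30 minutes after its end), per patient: Table 1 and footnote c give 0. One set with the EOI sample makes 1, or about 30 × 1 = 30 extra sets in the trial.

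**Timing of the added set.** The infusion lasts 15 ± 5 minutes, so 10 to 20 minutes (Protocol 5.5.1), and the EOI sample follows within 0 to 30 minutes.
- Earliest: 10 + 0 = 10 minutes after the start, study hour 0.17.
- Latest: 20 + 30 = 50 minutes after the start, study hour 0.83.

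**SAP 5.1 windowing.** The visit-window day is ceiling(study hour / 24), and one value per window is kept for mean summaries. The EOI set always maps to Day 1. The documents give no clock times, so these are assumed:

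| Dose | Day 2 reading | Hours from start | Window day |
|---|---|---|---|
| 16:00 | 06:00 | 14 | 1 |
| 08:00 | 08:00 | 24 | 1 (ceiling of 1.0) |
| 08:00 | 12:00 | 28 | 2 |

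A Day 2 morning reading taken 24 hours or less after dosing would therefore share a window with the EOI set, and one of the two would be dropped.

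**SAP 5.1 baseline.** Baseline is the last non-missing value on or before the dosing date, unless its time shows that it came after the dose. An EOI set without a recorded time could therefore become baseline.

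**Time still uncovered after the EOI set**, with dosing between 08:00 and 16:00 and a Day 2 reading between 06:00 and 12:00:
- Shortest: 14 h − 50 min = 13.2 h.
- Longest: 28 h − 10 min = 27.8 h.

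If the Day 2 reading is instead assumed to fall between 08:00 and 20:00, the first scheduled post-dose set comes 16 to 36 hours after dosing. Under either assumption, the acute window has no scheduled set today.

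**Precision of a dose-versus-placebo difference in mean systolic change.** There are 5 patients per dose and 3 × 5 = 15 pooled placebo patients, so 5 + 15 − 2 = 18 degrees of freedom.

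Half-width = t(0.975, 18) × SD × √(1/5 + 1/15) = 2.101 × 0.516 × SD = 1.085 × SD

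| Assumed SD of change (mm Hg) | 95% half-width (mm Hg) |
|---|---|
| 8 | 8.7 |
| 10 | 10.8 |
| 15 | 16.3 |

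The SDs are assumptions; the documents give none.

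**The case against.** The strongest reply is that the measurement is poorly matched to the risk. Section 2.1.4.2.3 describes typical acute reactions as mostly symptoms, and these are captured by the Day 1 AE assessment. Section 2.1.3.1 says: "In this fully pegylated prodrug form, bempegaldesleukin is inactive". Section 2.1.4.2.5 places the main haemodynamic effect later: "Instances of hypotension appear around 1-4 days following the infusion of bempegaldesleukin". Section 2.1.4.2.4 models the median peak heart-rate rise at 2.6 days for 0.006 mg/kg. The daily sets cover all of this. All of it stands, and it is why the gap is confined to the acute window.

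The protocol also expects blood-pressure monitoring beyond the schedule: sites must be equipped for it (5.5.4), hydration is titrated to hypotension (5.5.4.2), and antihypertensives may be restarted on the readings (5.12.2.2). Section 7.1 makes symptomatic or treated changes reportable, and Investigators are blinded (5.14). What goes unrecorded is therefore mainly asymptomatic, untreated and self-resolving change. That narrows the loss, but none of these provisions creates a planned, recorded measurement.

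The remedy is partial. One set after the infusion records nothing during it and can miss a brief change. Precision is coarse. Day 1 IV fluids, and premedication that "is recommended prior to bempegaldesleukin infusion at the discretion of the Investigator", may blunt a signal in both arms. This stands too. All the trial's analyses are descriptive, however, so one more descriptive time point is in keeping with the plan.

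**Conclusion.** The point holds as an optional improvement. The schedule places no vital-sign measurement in a period that the protocol itself names as one of two with the highest likelihood of adverse events; the change would take the count from 0 to 1 per patient.

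The count and the 10-to-50-minute timing follow from the documents, for a standard-length infusion. The uncovered hours rest on assumed clock times, and the 9-to-16 mm Hg half-width rests on assumed SDs. The reading covers the protocol and SAP only. The Pharmacy Manual and Investigator's Brochure, to which Section 5.5.2 refers for administration details, were not available and may specify monitoring.

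**What to change.** **Protocol.** Change the Day 1 vital-signs cell in Table 1 to predose and EOI. Reword footnote c, which read literally rules out a post-dose set on Day 1, to add one set (blood pressure, pulse, respiratory rate, SpO2, temperature) with the EOI PK sample. Time it within 30 minutes of the actual end of infusion, including an infusion that was prolonged or stopped early.

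**eCRF.** Record the clock time of the set so that it cannot be taken as baseline under SAP 5.1.

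**SAP 11.6.** Give Day 1 EOI its own hour-based nominal time point, from infusion start to 30 minutes after the actual end, so that it does not compete with a Day 2 reading that the ceiling rule maps to Day 1. That mapping exists already and would remain; it deserves its own correction.

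**Cost.** One table cell, one footnote, one timed eCRF record and one SAP time point, plus a few minutes per patient while staff are already drawing the EOI sample. No extra invasive procedure is needed. The change requires a protocol amendment with IRB/IEC review (12.1) at up to 10 sites, so it is best bundled with another amendment. The main new risk is an untimed EOI set becoming baseline. Scheduled sets cannot do that today because they are all predose, although an untimed unscheduled reading already could.
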